1. OBJECTIVES

To describe the acute and late complications from craniospinal and tumor bed irradiation using proton beam therapy in place of conventional photon beam therapy in pediatric patients with medulloblastoma and pineoblastoma.

1.1 Study Design

This trial is a phase II trial that substitutes proton irradiation for photon irradiation and measures toxicity from treatment. Because less normal tissue is irradiated it is presumed that it will be a less toxic treatment.

1.2 Primary Objectives

Analysis of primary objectives outcomes will be done separately for high risk and standard risk groups.

- 1.2.1 To estimate the incidence and severity of ototoxicity (especially in combination with cisplatin-based chemotherapy) at three (3) and five (5) years following the completion of radiation therapy.
- 1.2.2 To describe the incidence of endocrine dysfunction (neuroendocrine and end organ defects).
- 1.2.3 To describe the incidence and severity of neurocognitive sequelae overall and in subgroups based on whether or not methotrexate was used as part of the treatment regimen.

1.3 Secondary Objectives

- 1.3.1 To determine the 3 and 5-year progression free, event free, and overall survival rate of pediatric medulloblastoma and pineoblastoma patients treated with proton radiotherapy.
- 1.3.2 To develop a new supine technique to improve the speed of treating patients requiring cranial spinal irradiation and improve the safety of treating patients under anesthesia.
- 1.3.3 To evaluate the acute side effects from CSI using proton beam therapy, including nausea, esophagitis, and weight loss.

CONFIDENTIAL

[figure not shown]
This document is confidential. Do not disclose or use except as authorized.

2. BACKGROUND

2.1 Study Agent(s): Proton Radiotherapy

The current focus in radiation oncology is to improve dose localization to the tumor. Techniques such as Intensity Modulated Radiotherapy and Tomotherapy are two sophisticated photon techniques that have helped improve outcome in patients, however, there still remains a large amount of normal tissue getting low and intermediate doses of radiation. Proton radiation capitalizes on the different physical characteristics of dose deposition to better localize dose to the target while sparing normal tissues. Unlike photon radiation which entails both an entrance and exit dose to normal tissues in the process of treating a tumor in a given beam line, proton radiation only entails a somewhat lower entrance dose and eliminates exit dose to normal tissues. Proton therapy dose distributions are therefore superior to those of photon therapy by a factor of 2 or greater and this provides the potential to further improve clinical outcomes and specifically decrease toxicity associated with treatment.

2.1.1 The Advantages of Protons for Delivery of Conformal Therapy

Characteristics of Proton Beams

Figure O-1. Proton (Bragg peak and modulated peak) and 10 MV depth dose curves.

The basis for the advantages of proton beams lies in the physical laws that determine the absorption of energy in tissues exposed to photon or proton beams. In a specific tissue, photons are absorbed exponentially whereas protons have a finite range dependent upon the initial proton energy. Therefore, the depth dose characteristics of the two beams are qualitatively different (see Figure O-1). Protons lose their energy in tissue mostly by coulombic interactions with electrons in the constituent atoms; however, a small fraction of energy is transferred through nuclear collisions. The energy loss per unit path length is relatively small and constant as the proton traverses the tissue until near the end of the proton range where the residual energy is lost over a short distance (approximately 0.7 cm in width at 80% of the maximum dose) and the proton comes to rest, resulting in a

distinctive sharp rise in the tissue absorbed dose (energy absorbed per unit mass) - known as the Bragg peak (see the curve labeled "unmodulated proton beam" in Figure O-1). In physical terms, the magnitude of the transfer of energy to tissue per unit path length traversed by the protons is inversely proportional to the square of the proton velocity. The low dose region between the entrance and the Bragg peak is called the plateau of the dose distribution and the dose there is 30-40 percent of the maximum dose.

The Bragg peak is too narrow in extent to irradiate any but the smallest of targets, ablation of the pituitary gland for example. For the irradiation of larger targets/tumors the beam energy is modulated - several beams of closely spaced energies (ranges) are superimposed to create a region of uniform dose over the depth of the target. These extended regions of uniform dose are called "spread-out Bragg peaks" (SOBP). This is shown in Figure O-1 as the "modulated proton beam".

For comparison, Figure O-1 also shows the depth-dose curve for a 10 MV x-ray beam, an x-ray energy commonly used to treat deep seated tumors. Note that the x-ray beam dose rises to a maximum value at relatively shallow depths, then falls off exponentially to lower doses at the treatment depth.

[figure not shown]

Figure O-2. Posterior, single-beam treatment of the spinal axis.

A clinical comparison of single-beam proton and photon beams is shown in Figure O-2 where a single posterior beam is used for the treatment of the spinal axis in the treatment of medulloblastoma. Note that, for the photon treatment, the heart, mediastinum, esophagus, lung and spinal cord are irradiated by the treatment beam whereas for the proton treatment, the beam stops abruptly distal to the target volume and there is no irradiation of the tissues and organs distal to the target volume.

In the usual clinical situation, more than one radiation beam is used in both x-ray and proton treatments. However, the advantage shown for protons using single beams is present for each and every beam used. Therefore, one cannot overcome the physical disadvantage of x-rays by the use of multiple beams or complex beam arrangements. In modern proton therapy facilities, which have isocentric gantries and sophisticated beam delivery and control systems, proton therapy capabilities are equivalent to those for state-

of-the-art, conformal therapy using x-rays with respect to numbers of beams, beam directions and complex delivery techniques such as intensity modulation.

2.2 Study Disease

Primitive neuroectodermal tumors (PNET) are small hypercellular, round, blue cell tumors of embryonal origin arising from the subependymal zone of the central nervous system (CNS) [1]. Medulloblastoma (MB) and pineoblastoma (PB) are defined as PNET of the posterior fossa or pineal region respectively. These tumors tend to occur predominately in the pediatric population. MB and PB account for ~25% of CNS tumors in children. They have a propensity to spread to other regions of the CNS by subarachnoid seeding. Deutsch reported 46% incidence of CNS spread at presentation for pediatric MB [2]. Likewise, a 30% rate of positive neuraxis involvement was observed by Bloom et al [3]. Thus, approximately one-third of these patients present as high risk medulloblastoma and two-thirds as standard risk.

2.3 Rationale

The treatment of MB and PB of the central nervous system involves a multi-disciplinary approach. Surgery is necessary to obtain histological confirmation and to obtain maximal resection of tumor when feasible as the degree of resection correlates with outcome [4]. Patients are at risk for local and disseminated CNS recurrence even after gross total resection. Adjuvant therapy to the craniospinal axis is therefore essential. Craniospinal irradiation (CSI) is used in this setting for patients greater than 3 years of age. An additional boost of radiation encompassing the residual tumor and surgical bed is routinely given as this region is at highest risk for recurrence.

Photon CSI is associated with many possible acute and long-term sequelae:

Acute toxicity can include the following: bone marrow myelosuppression, fatigue, alopecia, headache, dermatitis, folliculitis, otitis externa, otitis media, anorexia, weight loss, nausea, vomiting, thrush, laryngitis, pharyngitis, esophagitis, gastritis, enteritis, cystitis, acute pericarditis, and temporary worsening of tumor associated neurological symptoms.

Prolonged myelosuppression and decreased bone marrow reserve may limit the ability to give chemotherapy after CSI. Somnolence syndrome is a subacute reaction associated with CSI often disabling the patient.

Long-term complications typically occur 3 months or more following completion of photon CSI and tend to be permanent. Complications arising from irradiation of the cranium include induction of second malignancy, permanent hair loss, cataract formation, retinopathy, sensorineural hearing loss due to damage to cochlea apparatus in inner ear, neuroendocrine dysfunction, and neuro-cognitive sequelae, rarely, necrosis and associated persistent vasogenic edema or atrophy. Adverse long term effects from photon irradiation of the spinal axis include: induction of second malignancy, stunting of growth of vertebral bodies and hypoplasia of paraspinal muscles and connective tissue resulting in scoliosis, kyphosis and decreased stature, spinal cord or nerve root damage, primary hypothyroidism, cardiomyopathy, pneumonitis, peptic ulcer disease, small and large bowel enteritis, primary ovarian failure, and decreased marrow reserve. These long-term sequelae can have

devastating effects in children on their future development and quality of life. Some of these complications are described in further detail below.

Ototoxicity:

Conductive hearing loss due to serous otitis media is a well-known acute reaction to RT and stems from mucositis causing blockage of Eustachian tube with transudation of serous fluid. Patients are at increased risk at doses > 40 Gy. Most cases resolve spontaneously.

Sensorineural hearing loss (SNHL) caused by damage to the cochlea and auditory nerve is a late complication from RT and can result in permanent hearing loss. While high doses of radiation are needed in the absence of chemotherapy to invoke SNHL [5-6], it can occur with lower radiation doses when ototoxic platinum chemotherapy agents are used. Evidence exists suggesting a dose response. Schoenthlaer et al reviewed 25 patients treated with high dose proton beam RT for base of skull tumors. Six patients developed decreased hearing acuity as a late complication. All patients with hearing loss received more than 60 cobalt gray equivalent (CGE) to at least 50% of the cochlea and auditory nerve [5]. In contradistinction, no patient receiving less than 60 CGE had hearing loss. Grai et al observed a higher incidence of severe SNHL in nasopharyngeal carcinoma patients receiving > 50 Gy to the inner ear compared to < 50 Gy [6]. Thibadoux et al found no hearing deficits in children receiving prophylactic cranial irradiation for acute lymphocytic leukemia [7]. Patients received 24 Gy in 2 Gy fractions. Hua et al studied the effect of cochlear dose on sensorineural hearing loss in children with brain tumors treated with conformal radiation therapy and no ototoxic chemotherapy. They found that there is significant correlation between radiation dose and the incidence of sensorineural hearing loss in children. Children with a cochlear mean dose of 30 Gy or less had a low incidence of hearing loss, while there was an increased risk at greater than 40-45 Gy [8].

Chemotherapeutic agents such as cisplatin and carboplatin can cause high frequency SNHL. Recent data suggests that the combination of chemotherapy (CTx) and RT can cause more serious ototoxicity. Packer et al from UCSF reviewed their pediatric MB patients treated with concurrent vincristine plus CSI followed by adjuvant cisplatin, CCNU and vincristine. They found 47.6% of patients developed grade 3 to 4 ototoxicity [9]. Twenty six MB pediatric patients treated at the Dana-Farber Cancer Institute (DFCI) with cisplatin and vincristine followed by CSI. Only 19% of patients had normal hearing and 50% of long term survivors required hearing aids [10]. Degree of hearing loss was inversely related to age. Sequencing of CTx and RT may also play a role in ototoxicity [11].

Neurocognitive toxicity:

Although the majority of CNS development occurs during the 1st 3 years of life, myelination continues until puberty. A major radiation insult on the CNS will result in demyelination with subsequent white matter necrosis and leukoencephalopathy. A large number of studies in the literature have documented decline in intellectual and cognitive functioning in children who have received whole brain radiotherapy (WBRT) for conditions including medulloblastoma, leukemia and other brain tumors [12]. The decline in functioning can be significant often necessitating placement in special education and a variety of therapeutic interventions. The effect of radiation depends upon the age of the child, with younger

children significantly more susceptible to the effects of radiation than older children, gender, with girls possibly more susceptible to decline in verbal function than boys, dose of radiation, with higher doses having more deleterious effects than lower, and time since completion of WBRT. This wide variability in these factors makes it difficult to formulate a clear post-treatment profile for children receiving WBRT.

IQ deficits following cranial irradiation range from 17 to 50%. The Children's Hospital of Philadelphia (CHOP) experience with cerebellar astrocytoma in children compared WBRT in 26 patients versus no RT in 21 patients. IQ declined by a median of 13 points in the irradiated group versus none in the observed group [13]. The volume of brain irradiated influences worsening of intellectual performance. Hoppe-Hirsch et al compared 59 children with MB who received WBRT to 37 children who received posterior fossa RT for ependymoma [14]. 60% of children with posterior fossa only irradiation preserved an IQ > 90 at 10 years of follow up. Conversely, only 10% with WBRT maintained an IQ > 90. Radiation dose also plays a role. Silber et al observed a higher drop in IQ below standard as dose of WBRT increased from 18 to \geq 36 Gy [15]. A study from Institut Gustave Roussy compared the neurocognitive outcome in 3 groups of pediatric patients who received different doses of radiation to the craniospinal axis. Group 1 consisted of 9 patients with ependymoma who received PF irradiation only, group 2 consisted of 11 patients with standard risk MB who received 25 Gy CSI plus PF boost and group 3 consisted of 11 patients with high risk MB who received 35 Gy CSI plus PF boost [16]. Increasing radiation doses to the brain were found to be correlated with lower full-scale IQ scores with mean IQ scores of 84.5, 76.9 and 63.7 for patients who had received 0 Gy, 25 Gy and 35 Gy to the non-PF brain. The Pediatric Oncology Group (POG) and Children's Cancer Group (CCG) have also compared reduced dose CSI at 23.4 Gy versus the standard 36 Gy dose in low stage pediatric MB patients. Chemotherapy was not used. A reduction in neuropsychologic toxicity was observed in the low dose arm especially in younger children [17], albeit with a higher local failure rate in the reduced CSI arm [18]. Packer et al compared 13 patients treated with WBRT plus cisplatin, CCNU, or vincristine versus 14 patients treated with surgery only for children with cerebellar astrocytoma [19]. WBRT dose was 36 Gy with a boost of 18-20 Gy for children 3 years or older. A decline in full-scale IQ was noted in the irradiated group. 12/18 patients required special education. The effect was most pronounced in younger children.

The cognitive decline in patients from CSI may also be enhanced by the addition of chemotherapy. Chemotherapy without radiation has been implicated as having neurocognitive effects. The best studied population is the ALL (acute lymphoblastic leukemia) population in which many children are never irradiated but still suffer neurocognitive effects. (Moleski, M. (2002) Neuropsychological, neuroanatomical, and neurophysiological consequences of CNS chemotherapy for acute lymphoblastic leukemia. Archives of Clinical Neuropsychology, 15, 603-630). Methotrexate, both high dose and intrathecal or intraventricular have been shown to cause leukoencephalopathy without radiation, but the addition of radiation appears to worsen outcome (Rutkowski et al, NEJM 352: 2005). However, the use of methotrexate chemotherapy in high doses does appear to improve disease free survival compared with standard regimens in infants and young children (Rutkowski et al, NEJM 352: 978-986, 2005; Chi et al, JCO 22: 2004) with medulloblastoma

and is increasingly gaining favor in the children with the higher risk disease. The other promising strategy is to deliver high dose chemotherapy with thiotepa and carboplatin with stem cell support and both treatment intensification strategies are employed in various institutions and cooperative group settings around the country and world.

Pituitary and hypothalamic toxicity:

Neuroendocrine dysfunction is extremely common following cranial irradiation in children and adults. Published data indicates a radiation dose response [20-22]. Littley et al showed that doses as low as 20 Gy to the hypothalamus and pituitary gland can cause hypopituitarism, primarily anterior lobe dysfunction [21]. Doses exceeding 50 CGE to the pituitary gland and hypothalamus using proton beam RT decreases the incidence of hypopituitarism [22]. Growth hormone deficiency is particularly common following cranial irradiation. Hypogonadism, hypoadrenalinism and hypothyroidism can also be observed. Patients often have more than one hormone axis involved. Life long monitoring for hypopituitarism and hormone replacement is often necessary.

Precocious puberty has been described in pre-pubertal patients treated with cranial irradiation [23]. The critical dose for precocious puberty is not well elucidated.

Thyroid gland toxicity:

Primary hypothyroidism after photon beam spinal axis irradiation has been well documented. 59% of patients developed elevated levels of TSH after spinal irradiation in a study by Hirsch et al [24]. A strong correlation between dose and incidence of hypothyroidism has also been demonstrated [24-26]. An incidence of 15% is noted for doses below 30 Gy; this increases to 40-90% for doses between 30 to 44 Gy [27]. For children, a study from Stanford University showed an incidence of 17% for doses < 26 Gy to the thyroid gland and 78% for > 26 Gy [25]. Radiation to the thyroid gland can also cause hyperthyroidism, although this is an uncommon event with a 10 year actuarial risk of < 3.5% [28]. Patients usually present with symptoms of Graves' ophthalmopathy.

Potential Benefits of Protons:

[figure not shown]
Benefits of spinal dose:

When a proton beam is applied for spinal irradiation, a single posteriorly directed proton beam delivers almost no dose to structures anterior to the treated volume compared to a standard photon treatment plan and even an IMRT plan. As shown in Figure O-2 (above), a direct comparison of a conventional 4 MV posteriorly directed field versus a single posteriorly directed 160 MeV proton beam to treat the spinal axis was made. Note the lack of exit dose to structures anterior to the vertebral bodies using protons compared to standard PA 4 MV photon plan. A comparative treatment plan of protons versus photons has also been published by Miralbell et al recently [29]. A 6 MV photon beam spinal field was compared to a 100 MeV proton beam spinal field. As expected, integral dose by DVH analysis to the heart and liver was zero using protons.

Benefits in cranial technique:

In a separate study, the same investigators were able to demonstrate advantages of a 3 field (2 opposed lateral and a posterior) proton plan for whole brain irradiation in a 3 year old child over parallel opposed 6 MV photon fields, 6 field conformal photon plan, or a 9 field IMRT photon plan [30]. A reduction in dose to the eyes and “low risk” regions of the brain was observed. The estimated risk of an IQ score < 90 in young children ages 4 to 8 was reduced using the proton plan. We have also compared lateral opposed conformal proton plan to standard lateral opposed photon plan and achieved similar benefit in improved dose distribution as noted by Mirabell et al. See figure O-3 below. The dose gradient is improved near the vertex of the head and decrease dose is delivered to the middle and inner ear regions using protons.

Figure O-3: Dose distribution to cranial fields in the Proton and Photon planned patient.

Furthermore, we have refined our technique and use slightly posterior oblique fields to better spare the lens while still achieving good coverage of the cribriform plate in the younger patients whose sinuses have not pneumatized yet and the brain therefore dips low and in between the orbits. Parallel opposed photon treatment places the child at high risk for cataract formation [31].

We have also demonstrated reduced normal tissue irradiation using protons for the posterior fossa boost field for medulloblastoma patients. A comparison between a conformal proton plan using 15 degree superior anterior oblique field with two 25 degree posterior oblique fields is compared to a comparable field set-up with conformal photons as described by Paulino et al [32], and to a standard lateral opposed 4 MV photon plan. As shown in table 1, a decrease in relative dose to the critical structures such as the cochlea, non-posterior fossa

brain, pituitary gland and hypothalamus is observed with conformal protons and conformal photons compared to that of conventional photons. However, extra dose is delivered to “less critical” normal structures such as the parotid gland and mandible using conformal photons as compared to conformal protons.

Table 1. Posterior fossa irradiation: Comparison of dose to normal structures using 3 different techniques [36]

Organ	% of Prescribed Dose (Dmean/Prescribed Dose)		
	6 MV lateral opposed photons (optimized with wedges)	SAO, RPO, LPO conformal photons	160 MeV SAO, RPO, LPO conformal protons
Cochlea	102.3	55.0	11.7
Non posterior fossa brain	47.1	40.6	26.1
Pituitary gland	80.1	91.1	57.2
Hypothalamus	15.8	47.2	35.0
Parotid Gland	38.8	32.2	0.0
Pharynx	7.3	8.9	0.0
Mandible	6.2	15.0	0.0
TMJ	59.7	33.9	0.0

Protons summary:

Superior dose conformity is therefore achieved with protons compared to other external beam modalities. Advantages in dose distribution are noted for all phases of CSI including spinal, whole brain and posterior fossa portions of treatment. The accuracy of delivering proton therapy is further enhanced by advancements in treatment planning and delivery technology. Improved radiological imaging with CT and MRI, the availability of computer technology for treatment planning and dosimetric calculations (e.g. beam’s eye view planning, 3-dimensional image reconstruction, dose volume histogram analysis) have contributed to enhancing the therapeutic ratio using radiation therapy. In other tumors and sites, comparative treatment planning using protons versus photons have shown a clear advantage to protons [33-35].

We have already treated 51 patients on the precedent medulloblastoma protocol with 37 standard risk patients and 14 high risk patients. We have found the following: acute esophagitis/mucositis rates are 12% which is lower than what would be expected which is close to 100% percent. Nausea and vomiting is still present but less severe than it would be for photon techniques in that we have a grade 2 rate of 26% and grade 3 rate of 12%. With regards to ototoxicity, since this is a late endpoint (after 3 years) we don’t have full data yet but preliminary data shows that we have 35% grade 2 hearing loss and a 9% grade 3 hearing loss rate. We have had 3 relapses thus far, 2 in the standard risk group and 1 in the high risk cohort. Disease control rates are comparable to those with photons. For the neuropsych

evaluations, there are only 18 patients in the database centrally that have both baseline and follow up data and no conclusions can be made based on the limited follow up to date. Additionally, more follow up data is being entered in the database.

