5.2.3 Target and Normal Structure Delineation

The following structures will be outlined on planning CT scans. It is recommended that the radiation oncologist outline the GTV. Cumulative dose volume histogram analysis will be completed for structures listed below:

- GTVp and surgical bed (see below for guidelines definitions)
- CTV1 and CTV2 (+/- CTV x...)
- Right and left cochlea
- Lenses
- Optic chiasm
- Pituitary gland
- Hypothalamus
- Esophagus
- Temporal lobes
- Whole brain

ICRU 50 and ICRU 78 [37] recommended terminology will be used to define radiation treatment parameters.

CTV1: Cranial-Spinal Treatment:

CTV1 shall be defined as the cranial spinal portion of the treatment and will include the entire cranial contents including cribriform plate and the thecal sac surrounding the spinal cord and nerve roots. Care should be taken to look at the sagittal spine MRI to define

where the thecal sac ends and an additional margin of 1-2 cm should be added to ensure coverage. When imaging is degraded or incomplete, coverage should extend to S4. The treating physician should use their judgment about whether the target will also include the vertebral body or only the thecal sac. However, in patients that have a significant amount of growth to do it is recommended that the whole vertebral body (or nearly so) be covered so as to avoid uneven growth of the vertebral body resulting in spinal scoliosis.

CTV2: Posterior Fossa or Involved Field Boost:

The GTVp is defined as any post-operative residual tumor seen on MRI or CT scan in addition to the collapsed resection cavity of the primary lesion.

The CTV2 is defined as 1-1.5 cm anatomically constrained margin around the GTVp and any other sites the treating physician judges to be at high risk for microscopically residual disease. Or, if the tumor is arising in the posterior fossa, the entire posterior fossa may be boosted. This is up to the COG protocol or physician discretion after consultation with the patient (if appropriate) or/and their guardians.

Metastases boosts:

Guidelines for boosting metastatic disease (ie M1, M2 or M3) will be in accordance with the COG guidelines and institutional practice, but are briefly outlined below.

CTV 3, 4, 5, etc:

The boosts for the gross metastatic deposits will be targeted with a 5-10 mm margin of CTV and include any other area the treating physician feels is at high risk for local recurrence.

Planning Target Volumes (PTV):

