Published data on neuroendocrine dysfunction and neurocognitive functioning have been based on small sample sizes, varying CSI doses and heterogeneous populations not directly comparable to the pediatric MB and PB patients in this protocol. Therefore, analysis of these endpoints will be focused mainly on estimation and precision. A standard-risk group of 48 patients will provide exact 95% confidence intervals of less than 30% for estimating the rates of neuroendocrine dysfunction and neurocognitive functioning, while the maximum interval width will be 46% based on 20 patients. Confidence intervals will be narrower in the analysis of acute effects, as more patients will be evaluable because very few losses will occur due to progression or death within 90 days following completion of CSI.

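### Section 2.3 and its Table 1 disagree on hypothalamic and pituitary dose; separately, the endocrine objective has no stated end-organ rate and the DVH list omits the thyroid

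*Combined protocol and SAP*

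**What the plan says.** In Section 2.3, under the benefits of the cranial technique, the protocol compares three ways of irradiating the posterior fossa. The text reads: "As shown in table 1, a decrease in relative dose to the critical structures such as the cochlea, non-posterior fossa" and continues "brain, pituitary gland and hypothalamus is observed with conformal protons and conformal photons compared to that of conventional photons". The table's first column is headed "6 MV lateral opposed photons (optimized with wedges"; the second is conformal photons and the third conformal protons. The row at issue is "Hypothalamus 15.8 47.2 35.0", as mean dose in percent of the prescribed dose. The summary that follows claims a proton advantage in every phase of treatment, the posterior fossa included.

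Primary objective 1.2.2 is "To describe the incidence of endocrine dysfunction (neuroendocrine and end organ defects"). For precision, Section 14.1 refers to "estimating the rates of neuroendocrine dysfunction and neurocognitive functioning" and does not mention end-organ defects. No section defines an endocrine event.

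Section 5.2.3 states "Cumulative dose volume histogram analysis will be completed for structures listed below". The list has the pituitary and hypothalamus but not the thyroid, and Section 5.2.5 generates DVHs for that list. Section 14.4 plans to explore normal-tissue DVHs as a factor in late complications. On thyroid dose, Section 2.3 cites a pediatric study that found "an incidence of 17% for doses < 26 Gy to the thyroid gland and 78% for > 26 Gy".

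**The concern.** Endocrine dysfunction is one of three primary objectives, and Table 1 is the protocol's own dosimetric evidence on the central axis. A reader who relies on the sentence will expect hypothalamic sparing in the boost; a reader who relies on the table will expect the reverse. The background to a primary objective should not give both.

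The second part concerns how the endocrine result can be read. The protocol gives different expectations by site. In the modelled boost, protons give more hypothalamic dose and less pituitary dose than conventional photons. In the spine, Section 2.3 expects almost no dose in front of the target, so the thyroid is where it expects sparing. An objective that names both kinds of defect, with precision stated for one and no event definition for either, leaves open what will be reported. Leaving the thyroid off the DVH list means that primary hypothyroidism has no planned dose variable, although the protocol itself calls its correlation with dose strong.

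**Working it through.** **1. The plan's own precision figures.** Section 14.1 states exact 95% interval widths below 30% for 48 patients and at most 46% for 20. The Clopper-Pearson interval is widest at half events: 24/48 gives 35.2% to 64.8%, width 29.5 points; 10/20 gives 27.2% to 72.8%, width 45.6 points. Both figures reproduce. They depend only on the number of patients, so they would hold equally for a separate end-organ rate if the same patients had data.

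**2. Sentence against table.** Four named structures and two conformal techniques give eight claimed decreases. Values are percent of prescribed dose; the ratio to conventional photons is in brackets.

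| Structure | Conventional photons | Conformal photons | Protons |
|---|---|---|---|
| Cochlea | 102.3 | 55.0 (0.54) | 11.7 (0.11) |
| Non-posterior-fossa brain | 47.1 | 40.6 (0.86) | 26.1 (0.55) |
| Pituitary | 80.1 | 91.1 (1.14) | 57.2 (0.71) |
| Hypothalamus | 15.8 | 47.2 (2.99) | 35.0 (2.22) |

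Five cells agree with the sentence. Three do not: hypothalamus with protons (35.0 − 15.8 = +19.2 points), hypothalamus with conformal photons (+31.4) and pituitary with conformal photons (+11.0).

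**3. What this means in total dose.** Table 1 covers posterior fossa irradiation only. Section 5.2.3 puts the whole cranial contents in the craniospinal target, so assume the hypothalamus and pituitary receive the full craniospinal dose. Then total = craniospinal dose + boost × Table 1 fraction. The craniospinal doses of 23.4 and 36 Gy and boosts of 18 to 20 Gy appear in Section 2.3 for cited studies; a 30.6 Gy boost is an added assumption to widen the range.

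- Hypothalamus, 23.4 + 30.6: protons 23.4 + 30.6 × 0.350 = 34.1 Gy; conventional photons 23.4 + 30.6 × 0.158 = 28.2 Gy; ratio 1.21.
- Hypothalamus, 36 + 18: 36 + 18 × 0.350 = 42.3 Gy against 36 + 18 × 0.158 = 38.8 Gy; ratio 1.09.
- The other combinations of 23.4 or 36 Gy with 18, 20 or 30.6 Gy lie between these two ratios.
- Pituitary, 23.4 + 30.6: 23.4 + 30.6 × 0.572 = 40.9 Gy with protons against 23.4 + 30.6 × 0.801 = 47.9 Gy, a reduction of 7.0 Gy.
- Pituitary, 36 + 18: 36 + 18 × 0.572 = 46.3 Gy against 36 + 18 × 0.801 = 50.4 Gy, a reduction of 4.1 Gy.

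All these totals exceed the 20 Gy at which Section 2.3 reports hypopituitarism.

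**4. Why separate rates read more clearly.** Suppose, for illustration only, that one any-defect rate were reported, that central and thyroid defects were independent, and that thyroid rates were the cited 78% and 17%. With central-defect rate c, the any-defect rate is 1 − (1 − c)(1 − t), and the difference between the two thyroid rates becomes (1 − c) × (78 − 17) = 61(1 − c) points. For c of 30, 50, 70, 80 and 90% this is 43, 31, 18, 12 and 6 points. The documents give no value of c; Section 2.3 says only that neuroendocrine dysfunction is extremely common after cranial irradiation.

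**The case against.** Much of the case on the other side stands.

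- A reader might infer that protons more than double hypothalamic dose. That ratio holds only for the modelled posterior fossa plan. In total dose it is about 1.1 to 1.2, and Section 5.2.3 also allows an involved-field boost, which Table 1 does not model.
- A reader might infer that no central benefit can be expected. The table does not support this: protons lower pituitary dose, and under the assumed doses the pituitary reduction (7.0 or 4.1 Gy) exceeds the hypothalamic increase (5.9 or 3.5 Gy).
- A reader might conclude that the table is right and the sentence wrong. The documents cannot settle that. The 15.8 may be a misprint, and the same paragraph calls the comparator a 4 MV plan where the table header says 6 MV.
- Pooling is nowhere mandated. Objective 1.2.2 names two components, Section 14.1 names one of them alone, and Section 6.1 lists hypothyroidism and neuroendocrine effects separately.
- A thyroid DVH is unplanned, not impossible, because Section 12.1.3 sends DICOM data for every patient to a central archive for analysis.
- Thyroid dose may vary little. Substitute photon spine dose is capped at 20%, or 7.2 Gy in the protocol's 36 Gy example, well below the cited 26 Gy.

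These points limit the size of the concern. They do not remove the text-table conflict, or the mismatch between an objective with two components and a plan that states precision for one.

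**Conclusion.** The contradiction in Section 2.3 is established by direct reading: three of eight cells go against the sentence, including hypothalamic dose with protons. By itself it is an error in the background, and which side is wrong cannot be determined from the documents.

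The two changes to the endocrine plan are inexpensive improvements. Objective 1.2.2 covers end-organ defects that Section 14.1 does not carry through, and Section 14.4 calls for normal-tissue DVHs while Sections 5.2.3 and 5.2.5 leave out the end organ with a dose-response that the protocol describes as strong.

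It is tempting to conclude that the proton effect on endocrine outcome is obscured. The documents do not support that: there is no photon arm and no endocrine hypothesis, the analysis is mainly estimation, and a single pooled rate is only one possible reading. The hearing-loss decision rules and their power are untouched. The total-dose ratios rest on the assumed doses and on full craniospinal dose to the hypothalamus and pituitary; the dilution figures rest on an assumed composite, independence and assumed central rates.

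**What to change.** 1. Reconcile the Section 2.3 sentence and Table 1 with the cited source, without presuming which is wrong. Settle the 4 MV and 6 MV description of the comparator at the same time, and adjust the summary claim for the posterior fossa if the table stands.
2. In Sections 1.2.2, 14.1 and 14.4, report central (hypothalamic-pituitary) and primary end-organ dysfunction as separate rates, each with its exact 95% interval and by risk group. Use TSH and free T4, where collected, to separate primary from central hypothyroidism. State how many patients have follow-up laboratory data: Section 9.2.1 requires these tests at baseline but only recommends them annually, so the intervals may be wider than Section 14.1 states.
3. Add the thyroid to the contour and DVH list in Section 5.2.3, and use its dose, including any photon fractions, in the exploratory Section 14.4 model for primary hypothyroidism.

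The cost is wording, two endocrine rates in place of one, and one more contour per plan on planning CTs that already exist. No new patient procedure is needed.
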